## **8. EFFICACY**

### **8.1. General Considerations**

All statistical analyses will be conducted using statistical analysis system SAS® Version 9.4 or higher (SAS Institute, Cary, NC).

Analysis of the data from this study will be descriptive in nature. N, mean, standard deviation, first quartile, median, third quartile, minimum, and maximum will be used for continuous data and number and percentage will be used for categorical data, unless specified otherwise.

Mean, median and quartile data will be presented to one decimal place, standard deviation will be presented to two decimal places.

### **8.2. Timing of Analyses**

After the Lead-in group is enrolled and reaches the 4 weeks post-treatment time point, the lead-in group will be evaluated for safety, sustained virologic response at 4 weeks posttreatment (SVR4) and virologic relapse.

Once the enrollment of the main study is completed, and the subjects reach the 12 weeks post treatment (SVR12) the database will be frozen and the primary analysis will be conducted – this primary analysis may serve as the basis for a CSR.

Once all subjects reach the 24 weeks post-treatment, the secondary analyses (i.e. SVR24 related efficacy endpoints and applicable safety after 12 weeks post-treatment) will be conducted. These secondary analyses may be used as the basis for an Addendum to the CSR.

### **8.3. Testing Statistical Assumptions Including Comparability at Baseline**

This is a one arm study. No statistical tests will be performed.

### **8.4. Statement of the Null and Alternate Hypotheses**

No statistical test is planned.

### **8.5. Subgroup Analyses**

Subgroup analysis will be performed according to the following baseline characteristics:

- HCV genotype (HCV GT1, GT2, GT3, GT4, GT5, GT6 or GT7)
- Cirrhotic status (non-cirrhotic, compensated cirrhosis)
- Fibrosis stage (F0, F1, F2, F3, or F4)
- Baseline resistance-associated variants
- Baseline viral load

## **8.6. Multiple Comparisons and Multiplicity**

No statistical tests will be performed; therefore, considerations of multiplicity are not necessary.

## **8.7. Analysis of the Primary Efficacy Endpoint**

### **8.7.1. Laboratory Result-Based Efficacy Derivations**

Efficacy will be determined by HCV RNA results at the relevant timepoints. Each timepoint will have one result for the HCV RNA. In the event that multiple values are present within the window for the timepoint, the latest value will be used. In the event that the timing of duplicate or repeat HCV RNA values is the same, the result with the alphanumerically lowest accession number will be used.

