### **5.6. Stopping Rules**

#### **5.6.1. Individual Virologic Stopping Rules**

Treatment will be discontinued in any subject with on-treatment virologic failure, defined as any one of the following:

- Confirmed  $1 \log_{10}$  increase in HCV RNA from post-baseline nadir
- Confirmed increase in HCV RNA  $\geq$  LLOQ in any subject who achieved HCV RNA  $<$  LLOQ

Confirmation should be performed as soon as possible after an initial HCV RNA value that may indicate virologic failure is reported.

After completion of study-related procedures in the current study, the investigator may offer an approved poststudy HCV treatment regimen consistent with local standard-of-care treatment guidelines to subjects who have on-treatment virologic failure or posttreatment virologic relapse. For those subjects who generally comply with the study protocol and experience lack of efficacy (failure to achieve SVR12 or SVR24) with the investigational regimen, the Sponsor may reimburse the investigator for the cost of a course of poststudy medication depending on local drug access and reimbursement policies.

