a Screening window may be extended to 42 days for extenuating circumstances with Sponsor approval.

b Day 1 assessments performed prior to dosing.

c The last dose is on Day 56. The last visit of the treatment period shall occur no sooner than Day 57 and no later than Day 60 (inclusive).

d Three consecutive determinations collected, with no less than 1 minute between individual ECGs. Complete ECGs prior to any blood draws.

e For females of childbearing potential, serum or urine is acceptable.

f Plasma samples collected for resistance testing. At least one baseline resistance sample is needed (Screening and/or Day 1 predose); there is no protocol deviation if there is one evaluable baseline sample for resistance testing. In addition, the resistance sample is not required for screening and eligibility purposes.

g On Day 1, the PK sample will be obtained predose. The sampling time and time of last dose must be recorded.

h See Table 3

i Subjects may be contacted between visits to assess compliance, concomitant medications, and AEs/SAEs.

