### 6.7.4. Visit Windows

For the purposes of by-visit analyses for scheduled clinical assessments (i.e., excluding patient-reported assessments), visit windows for inclusion in the analysis are defined in Table 4. Note that the definition of baseline is provided in Section 6.

Early termination data will be mapped based on the scheduled Study Day of each scheduled visit as specified in the protocol schedule of events.

Visits assigned as “unscheduled” by labs for safety data and HCV RNA quantitation will be mapped based on the table below. If there is more than one unscheduled visit in a visit window, the visit closest to the target date will be used in by-visit analyses. If there is a tie between the number of days from the target date, the later visit will be used. Unscheduled visits that fall within the protocol-defined visit windows will be summarized in the by-visit analyses only if there is no scheduled visit available in the analysis visit window.

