### **6.7.5. Multiple Assessments**

If multiple assessments are obtained within a visit window for a subject, the value obtained closest to the target timepoint will be used. For any visit, no more than one value per subject will be included in an analysis. In the event of multiple observations that are equidistant from the target day (e.g., two observations on the same day or observations made in a similar time frame before and after target), the earliest value, based on date and time, will be selected.

Multiple efficacy assessments will follow the rules outlined in section 8.7.1.

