#### **8.7.2.1. On-Treatment Virologic Failure**

On-treatment virologic failure is defined as any of the following, while on-treatment:

- Not achieving  $\text{HCV RNA} < \text{LLOQ}$
- Confirmed 1  $\log_{10}$  increase in HCV RNA from post-baseline nadir (would call this “virologic rebound” if we want to name it in parenthesis)
- Confirmed increase in  $\text{HCV RNA} \geq \text{LLOQ}$  in any subject who achieved  $\text{HCV RNA} < \text{LLOQ}$

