#### **8.7.2.2. Post-Treatment Relapse**

Post-Treatment Relapse is defined as  $\text{HCV RNA} \geq \text{LLOQ}$  after treatment discontinuation in a subject who completed the treatment regimen (at least 51 days) and who had  $\text{HCV RNA} < \text{LLOQ}$  at the time of treatment discontinuation.

Note: Week 8 HCV RNA should be considered “on-treatment” in any subject who received 51 or more days of treatment.

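### SAP 8.7.1 keeps one HCV RNA value per window without saying that confirmation of virologic failure is judged first, and a first rise at Week 8 fits neither failure type in SAP 8.7.2

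*SAP*

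**What the plan says.** **Reduction to one value.** SAP 8.7.1 states "Each timepoint will have one result for the HCV RNA" and "In the event that multiple values are present within the window for the timepoint, the latest value will be used". SAP 6.7.5 gives a different general rule (closest to target, then earliest) but hands efficacy over: "Multiple efficacy assessments will follow the rules outlined in section 8.7.1". SAP 6.7.4 maps unscheduled HCV RNA samples into the Table 4 windows and uses them in by-visit summaries "only if there is no scheduled visit available in the analysis visit window".

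**Failure types.** SAP 8.7.2 recognises two types of virologic failure. For the first, SAP 8.7.2.1 says "On-treatment virologic failure is defined as any of the following, while on-treatment" and lists three alternatives: never reaching a value below LLOQ, a confirmed 1 log10 rise from nadir, and a confirmed return to LLOQ or above. For the second, SAP 8.7.2.2 requires completed treatment (at least 51 days) and a value below LLOQ "at the time of treatment discontinuation". The same section treats the Week 8 sample as on-treatment after 51 or more days of dosing.

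**Secondary endpoint.** SAP 8.8 defines virologic failure by the two confirmed criteria alone, with no on-treatment limit.

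**Timing.** Protocol 5.6.1 says "Confirmation should be performed as soon as possible after an initial HCV RNA value that may indicate virologic failure is reported". Protocol Table 2, footnote c, puts the last dose on Day 56 and the Week 8 visit on Days 57 to 60.

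**The concern.** Confirmation needs a pair of values, and the derivation rule keeps one per window. If the failure flag is programmed on the reduced data, a subject whose rise was repeated promptly can lose the label that the repeat was meant to establish, while a subject repeated a few days later keeps it. The label would then depend on sampling logistics.

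The Week 8 case is a gap in the definitions themselves. A subject below LLOQ at Week 6 and at or above LLOQ from Week 8 onward has failed SVR12, yet on a plain reading belongs to neither of the two types in SAP 8.7.2.

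Virologic failure is a secondary endpoint (SAP 3.2.2, 8.8), selects the subjects in the emergent-RAV analyses (SAP 8.9), and drives the lead-in decision (SAP 4.1, 5.1). SAP 5.1 defines failure there as on-treatment failure or relapse by post-treatment Week 4, so a subject who fits neither type would not be counted.

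**Working it through.** The plan gives no figure of its own on this point, so the check applies the SAP rules as written to hypothetical histories. Positive means at or above LLOQ, negative means below LLOQ, and EOT = Day 56 for a completed course.

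**Step 1: how long each window stays open.** Days left = upper limit in SAP Table 4 minus the sample day. Visit days come from Protocol Table 2.

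| Visit | Window | From target day | Over allowed visit days |
|---|---|---|---|
| Week 1 | 2–11 | 11 − 8 = 3 | 2–4 |
| Week 2 | 12–21 | 21 − 15 = 6 | 5–7 |
| Week 4 | 22–35 | 35 − 29 = 6 | 3–9 |
| Week 6 | 36–49 | 49 − 43 = 6 | 3–9 |
| Week 8 | 50–(56 + 20 = 76) | 76 − 57 = 19 | 16–19 |

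A repeat within these limits shares the window with the initial value. Under 8.7.1 the repeat stays and the initial value goes. Week 1 matters little, because it is the first scheduled post-baseline sample outside the PK-VK substudy.

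**Step 2: apply the latest-value rule, then 8.7.2.** The last two columns differ in whether an off-treatment value may confirm.

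| History | Values kept | On-treatment confirmation only | Off-treatment may confirm |
|---|---|---|---|
| (a) Negative Day 43; positive Days 57, 84, 140 | All | Neither type | On-treatment failure |
| (b) As (a), plus positive repeat Day 61 | Day 61 replaces Day 57 | Neither type | On-treatment failure |
| (c) Negative Day 15; positive Days 29 and 33; no later sample | Day 33 only | Unconfirmed | Unconfirmed |
| (d) As (c), plus positive ET sample Day 38 | Days 33 and 38 | On-treatment failure | On-treatment failure |
| (e) As (c), but repeat on Day 37 instead of Day 33 | Days 29 and 37 | On-treatment failure | On-treatment failure |
| (f) Never negative through Week 8 | All | On-treatment failure, no confirmation needed | Same |

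Histories (c) and (e) differ only in a repeat four days later (37 − 33). History (c) contains no follow-up sample. A positive one would confirm it only if off-treatment confirmation is allowed.

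**Step 3: the Week 8 case against each definition.**
- 8.7.2.1: after Week 8, the next window opens at EOT+21 = Day 77 and is post-treatment. No later on-treatment window exists to confirm the rise.
- 8.7.2.2: the Week 8 sample counts as on-treatment and is positive, so the subject was not below LLOQ at discontinuation. Relapse is excluded.
- 8.8: Week 8 and Post-Treatment Week 4 are separate windows, so both values survive. With no on-treatment limit, the case is virologic failure if a post-treatment value may confirm.

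**Step 4: what one unlabelled subject does.**
- Lead-in, if all 60 are evaluable: 7/60 = 11.7% closes enrolment; 6/60 = 10.0% opens it.
- Secondary failure rate with 266 evaluable: 1/266 = 0.38 percentage points.
- Emergent-RAV denominator: if 3% to 5% of 266 fail (an assumption; the documents give no expected rate), there are about 8 to 13 failures (266 × 0.03 = 8.0; 266 × 0.05 = 13.3), and one subject is 1/13 = 8% to 1/8 = 13% of them.

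These are effects per subject, not estimates of how many are affected.

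**The case against.** The best defence is that the SAP need not be read this way. Section 8.7.1 sits under the primary endpoint and concerns results at timepoints; nothing says the failure flag is built on windowed data. Section 8.7.2.1 does not say the confirming sample must itself be on treatment. The only definition of a confirmed value, written for safety laboratory tests in Protocol 5.6.2, refers to the next test with no window or dosing limit. Section 8.8 would then capture the Week 8 case. SAP 3.2.3 also refers RNA-related derivations to Appendix 1, which is not available here. All these readings are possible, but the SAP text available here states none of them, and 8.7.2.1 opens with an on-treatment limit.

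The second defence is that loss is uncommon. Protocol 5.6.1 runs the repeat from when the result is reported, samples go to a central laboratory (Protocol 6.6), and no turnaround time is given. A reader might infer that prompt repeats usually share a window with the initial value; the documents do not show that. Protocol 5.7 also asks for an ET visit after early discontinuation, and an ET sample in the next window restores the pair, as in history (d). This stands, and it limits the size of the problem.

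The third defence is that the study is descriptive with no hypothesis tests (SAP 8.4, 8.6). That is true, but the lead-in count is still a decision rule.

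**Conclusion.** The point holds in a limited form. The SAP states a one-value rule and failure criteria that need two values, and does not say which comes first. It also leaves a first rise at Week 8 outside both types in 8.7.2, while 8.8 may count it. It should be settled before database lock but does not threaten the primary result.

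Four stronger inferences are not supported:
- **All on-treatment failure needs confirmation.** Never reaching a value below LLOQ does not.
- **The repeat is discarded.** 8.7.1 keeps the latest value, so the initial one is dropped. The by-visit rule in 6.7.4 could drop an unscheduled repeat, but 6.7.5 sends efficacy to 8.7.1.
- **A Week 8 case disappears from every failure count.** Under 8.8 it can still count.
- **SVR12 is distorted.** SAP Table 5 takes SVR12 from the 12- or 24-week result, a positive EOT or post-treatment Week 4 result, or the discontinuation category, not from the 8.7.2 labels.

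The conclusion rests on a literal reading of 8.7.1 and 8.7.2.1 and, for the Week 8 window, on EOT = Day 56. The number of subjects affected cannot be derived and is likely to be few.

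**What to change.** Four changes to the SAP, for analysis only; the protocol's individual stopping rules stay as they are:
1. In 8.7.1, limit the one-result rule to SVR at a timepoint and to by-visit viral-load summaries.
2. In 8.7.2.1, state that confirmation is assessed on all HCV RNA records in date order, before windowing.
3. State that a first value at or above LLOQ at Week 8 counts as on-treatment virologic failure if the next available result, on or off treatment, is also at or above LLOQ.
4. Align the virologic failure definition in 8.8 with 8.7.2, including the criterion of never reaching a value below LLOQ, which 8.8 omits.

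Allowing off-treatment confirmation alone would settle histories (a) and (b) but not (c); change 2 is needed for that.

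The cost is a few sentences and a change to the programming of the failure flag. No new data are needed.

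### Using the latest HCV RNA value in the wide Table 4 windows can turn an early relapse sample into the on-treatment Week 8 value, and can replace a scheduled 12-week result with a much later one

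*SAP*

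**What the plan says.** SAP 6.7.4 allocates unscheduled HCV RNA samples to analysis visits: "Visits assigned as “unscheduled” by labs for safety data and HCV RNA quantitation will be mapped based on the table below". SAP 6.7.5 has a general rule for several values in one window, under which "the value obtained closest to the target timepoint will be used", but it makes an exception for efficacy: "Multiple efficacy assessments will follow the rules outlined in section 8.7.1". The efficacy rule in 8.7.1 is: "In the event that multiple values are present within the window for the timepoint, the latest value will be used". It gives no priority to a scheduled visit and takes no account of distance from the target day.

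SAP Table 4 sets the windows. Week 8 (target Day 57) runs from Day 50 to EOT+20. Post-treatment Week 12 (target EOT+84) runs from EOT+70 to EOT+146. In the protocol, EOT is the day of the last dose, planned for Day 56. The Week 8 visit falls on Days 57 to 60, and the follow-up visits have a margin of 5 days either way (protocol Table 2 and its footnotes).

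SAP 8.7.2.2 defines relapse as a quantifiable HCV RNA after treatment in a subject who completed at least 51 days and was below LLOQ when treatment ended. Its note counts Week 8 HCV RNA as on-treatment "in any subject who received 51 or more days of treatment". SAP 8.7.2.1 recognises an on-treatment failure after suppression only if the rise is confirmed.

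**The concern.** A latest-value rule does little harm when windows are narrow. Here they extend well past the scheduled visits, with two consequences.

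First, a sample taken up to 20 days after the last dose can become the Week 8 value and so carry on-treatment status. A subject who was suppressed at the end of treatment and relapsed early may then no longer qualify as a relapse. Protocol 8.4.1 plans a summary of reasons for not achieving SVR12. The split between on-treatment failure and relapse is central to judging an 8-week course, because relapse after suppression is the pattern expected if treatment was too short.

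Second, SVR12 is meant to be response at 12 weeks post-treatment (protocol synopsis, Criteria for Efficacy), with SVR24 as a separate endpoint. In a subject with an additional sample, SVR12 could be read at almost 21 weeks even though a valid 12-week sample exists. Whether that happens depends on who has an extra sample drawn.

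**Working it through.** **Week 8 window.** With the last dose on Day 56, EOT+20 is 56 + 20 = Day 76. The scheduled visit on Days 57 to 60 is EOT+1 to EOT+4, so a sample from EOT+5 to EOT+20 is later than any permitted end-of-treatment visit yet still maps to Week 8.

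Example: Day 57 below LLOQ; unscheduled Day 72 (72 − 56 = EOT+16) at or above LLOQ.
- 8.7.1 takes the Day 72 result as the Week 8 value.
- The note in 8.7.2.2 makes that value on-treatment.
- If Week 8 supplies the status at discontinuation, the subject was not below LLOQ then and fails the relapse definition.
- If the rise is confirmed, the subject can be counted as an on-treatment failure. If not, the subject fits neither category.
- With the scheduled Day 57 sample as the status at discontinuation, the subject is a relapse.

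SVR12 is read from the Week 12 sample, or the Week 24 sample if that is missing (SAP Table 5), so this example does not change it. The combined virologic failure endpoint in 8.8 is also unchanged if the rise is confirmed.

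**Week 12 window.**
- Length: 146 − 70 + 1 = 77 days, against 11 days for a visit allowed 5 days either side; 77/11 = 7.0.
- Reach past target: 146 − 84 = 62 days; 146/7 = 20.9 weeks post-treatment.
- Protocol Table 2 counts follow-up from the last treatment visit (EOT+1 to EOT+4). The latest permitted Week 12 visit is therefore between 1 + 84 + 5 = EOT+90 and 4 + 84 + 5 = EOT+93. The window extends 146 − 93 = 53 to 146 − 90 = 56 days beyond it.

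| Scheduled sample | Later unscheduled sample | Latest value (8.7.1) | Scheduled value |
|---|---|---|---|
| EOT+84, < LLOQ | EOT+140, ≥ LLOQ | failure | SVR12 |
| EOT+84, ≥ LLOQ | EOT+98, < LLOQ | SVR12 | failure |

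The second row cannot occur if other HCV treatment started before the later sample, because SAP 8.7.3 then imputes failure.

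**Scale.** The planned sizes reproduce: 280 × 0.95 = 266 and 75 × 0.95 = 71.25, taken as 71. The bounds in SAP Table 3 reproduce as one-sided 95% Wilson lower limits, [p + z²/2n − z√(p(1−p)/n + z²/4n²)] / (1 + z²/n) with z = 1.645. For 68/71 this gives 89.89%, printed as 90%; for 67/71 it gives 88.03%, printed as 88%.

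- One reversed subject: 1/266 = 0.38 points overall; 1/71 = 1.41 points in genotype 3.
- Genotype 3, 68/71 to 67/71: the rate falls from 95.77% to 94.37%, and the one-sided bound from 89.89% to 88.03%.
- Overall, from 253/266 = 95.11% (two-sided 95% Wilson interval 91.82 to 97.12): one reversal to failure gives 252/266 = 94.74% (91.36 to 96.84); five give 248/266 = 93.23% (89.56 to 95.68).

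The starting counts and the range of one to five reversals are assumptions for illustration.

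**The case against.** A reader might infer that 6.7.4 and 8.7.1 contradict each other and leave SVR12 undefined. The documents do not support that. SAP 6.7.5 assigns repeated efficacy values to 8.7.1. The scheduled-first sentence in 6.7.4 is also narrower than it looks: "Unscheduled visits that fall within the protocol-defined visit windows will be summarized in the by-visit analyses only if there is no scheduled visit available". It concerns by-visit summaries and unscheduled visits inside the protocol-defined windows. Samples at EOT+16, EOT+98 or EOT+140 lie outside those windows, so it does not plainly reach them.

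The latest-value rule is also prespecified and leaves the analyst no discretion. It counts a documented recurrence as failure, which is unfavourable to the regimen. It fits the backward imputation in 6.8.1 and the use of the 24-week result in Table 5 when the 12-week result is missing. Adjoining windows give every sample a place. These points stand, and they make the Week 12 change partly a matter of preference. What remains is that Table 5 turns to later data only when the 12-week result is absent, whereas 8.7.1 lets later data displace one that is present.

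On Week 8, 8.7.2.2 does not say that status at discontinuation is the Table 4 Week 8 value. On its plain wording, a Day 57 result could qualify and the subject would be a relapse. That is a fair reading, but the SAP does not state it. The one-value-per-timepoint rule together with the on-treatment note points the other way, so the classification depends on the programmer.

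**Conclusion.** The point holds in two parts. The Week 8 part is the firmer: a sample from EOT+5 to EOT+20 can take on-treatment status and remove an early relapse from the relapse category. The harm is confined to the reasons-for-failure split. It would go too far to say that such a relapse always becomes an on-treatment failure, since that requires confirmation.

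The Week 12 part is a weaker objection to a prespecified choice. The SVR12 reading can move up to 62 days past target, about 53 to 56 days beyond the latest permitted visit, in either direction subject to 8.7.3. The effect is 0.38 points per subject overall and 1.41 points in genotype 3.

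The total effect cannot be sized, because the number of unscheduled samples is not stated. A reader might also assume that post-treatment unscheduled samples are drawn mainly when something looks wrong. The documents do not say so; the prompt repeat testing in protocol 5.6.1 concerns on-treatment failure. The study is descriptive with no hypothesis test (SAP 8.4), so what is at stake is the reported estimates and failure categories.

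**What to change.** 1. In SAP 8.7.2, set on-treatment or post-treatment status for HCV RNA by sample date relative to the last dose. Take status at treatment discontinuation from the scheduled end-of-treatment sample (Days 57 to 60, EOT+1 to EOT+4 for a Day 56 last dose). Treat later samples as post-treatment when classifying relapse. State that a quantifiable value from EOT+5 to EOT+20 still counts as positive in the Table 5 column for EOT or post-treatment Week 4, so that a subject with no 12- or 24-week sample remains a failure and is not excluded.

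2. In SAP 8.7.1, derive SVR12 from the scheduled Week 12 sample or, if there is none, from the sample closest to EOT+84, and report a later recurrence as late relapse. If the latest-value rule is kept for the primary analysis, add this derivation as a sensitivity analysis. If a repeat test may overturn a scheduled result at or above LLOQ, say so and give the permitted interval.

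The cost is SAP text and programming, with no new data. The drawback of the second change is that a recurrence after the scheduled visit but inside the window would no longer count as an SVR12 failure, so late relapses need their own line in the results.
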